		
TEAE identified by the investigator PT within HLT: by maximum severity, by maximum redness category, by maximum swelling category, by maximum pain category
 
Listing: TEAE including information collected on Injection Site Reaction eCRF page

Cerebro-cardiovascular Events	
Cerebro-cardiovascular events will be externally adjudicated by the Clinical Events Committee (CEC) at the Cleveland Clinic, as outlined in the Manual of Operations. Investigator-reported events will be selected for adjudication, based on the assigned MedDRA PT and the criteria outlined in the listing provided in Appendix 9 of the IXE PSAP V7. The CEC will adjudicate investigator-reported events selected for adjudication and render an assessment as to whether the event represents a confirmed event (meeting the event definition with all necessary documentation), a non-event (does not meet the event definition and likely represents an alternative or nonevent diagnosis), or lacks sufficient documentation for confirmation of an event. All events which qualify for CEC adjudication will be used for the analysis of cerebro-cardiovascular events. The categories of adjudicated events used for the analysis will include the following:
 
 • Cardiovascular 
 ○ Death (Cardiovascular) ○ Myocardial Infarction (MI) ○ Hospitalization for Unstable Angina ○ Hospitalization for Heart Failure ○ Serious Arrhythmia ○ Hospitalization for Hypertension 	
Period 2 (Fisher’s exact test): TEAE by PT within Subcategory, SAE by PT within Subcategory, AE leading to treatment discontinuation by PT within Subcategory
 
Period 3 (Summary): TEAE by PT within Subcategory, SAE by PT within Subcategory, AE leading to treatment discontinuation by PT within Subcategory
 
Listing: TEAE

Special Safety Topic	Definition / Derivation	Analysis / Summary / Listing
	
 ○ Resuscitated Sudden Death ○ Cardiogenic Shock due to Myocardial Infarction ○ Coronary Revascularization Procedure ● Neurologic 
 ○ Cerebrovascular Event: Transient Ischemic Attack or Stroke (Hemorrhagic, Ischemic and Undetermined) ● Peripheral Vascular Events 
 ○ Peripheral Arterial Event ○ Peripheral Revascularization Procedure 
Events will be analyzed using MedDRA PT nested within the CEC assessment (confirmed event, no event, or insufficient documentation for event determination) and the subcategory. Subtypes of stroke (Hemorrhagic Stroke, Ischemic Stroke, and Undetermined Stroke Type) will be displayed in the analyses nested within Cerebrovascular Event. Subtypes of Serious Arrhythmia (Atrial Arrhythmia, Ventricular Arrhythmia, Heart Block, Other, Unknown) will be displayed nested within Serious Arrhythmia.
	
Major Adverse Cardiovascular Events (MACE)	
Major Adverse Cerebro-Cardiovascular Events (MACE) in general are a subset of the cerebro-cardiovascular events (requiring adjudication as defined above). MACE events are defined as follows (see Appendix 9 of the IXE PSAP V7):
 
 ● Vascular Death (including cardiovascular and cerebro-vascular causes excluding hemorrhagic deaths outside of the central nervous system) ● Non-fatal myocardial infarction ● Non-fatal stroke (subtypes: hemorrhagic stroke, ischemic stroke, undetermined stroke type) 	
Period 2 (Fisher’s exact test): TEAE by maximum severity by PT within Category
 
Period 3 (Summary): TEAE by maximum severity by PT within Category
 
Listing: TEAE

Malignancies	
Malignancy is defined using PTs from the Malignant or unspecified tumors SMQ as specified in MedDRA (SMQ: 20000091, which includes the sub-SMQs: 20000195 [Tumours of unspecified malignancy] and 20000194 [Malignant tumours]).
 
Events will be summarized by the following categories:
 
 ● Non-Melanoma Skin Cancer (NMSC) 
 ○ Basal Cell Carcinoma, PTs include: 	
Period 2 (Fisher’s exact test): TEAE by PT within Category, SAE by PT within Category, AE leading to treatment discontinuation by PT within Category

Special Safety Topic	Definition / Derivation	Analysis / Summary / Listing
	
 ▪ Basal cell carcinoma ▪ Basosquamous carcinoma ▪ Basosquamous carcinoma of skin ○ Squamous Cell Carcinoma, PTs include: 
 ▪ Squamous cell carcinoma of skin ▪ Bowen’s disease ▪ Lip squamous cell carcinoma ▪ Skin squamous cell carcinoma metastatic ▪ Keratoacanthoma • Malignancies excluding NMSC: all PTs in the Malignant or unspecified tumors SMQ excluding the 8 defined NMSC PTs. 	
Period 3 (Summary): TEAE by PT within Category, SAE by PT within Category, AE leading to treatment discontinuation by PT within Category
 
Listing: TEAE

Depressions and Suicide/Self-injury	
Depression is defined using the PTs from the Depression and suicide/self-injury SMQ as specified in MedDRA (SMQ: 20000035, which includes the sub-SMQs: 20000037 [Suicide/self-injury] and 20000167 [Depression (excl suicide and self- injury)]).
	
Period 2 (Fisher’s exact test): TEAE by PT within SMQ and sub-SMQ, SAE by PT within SMQ and sub-SMQ, AE leading to treatment discontinuation by PT within SMQ and sub-SMQ
 
Period 3 (Summary): TEAE by PT within SMQ and sub-SMQ, SAE by PT within SMQ and sub-SMQ, AE leading to treatment discontinuation by PT within SMQ and sub-SMQ
 
Listing: TEAE

Interstitial Lung Disease (ILD)	
ILD is defined using the following terms:
 
 • Broad and narrow terms in the Interstitial lung disease SMQ (20000042) • Additional 6 PTs from Eosinophilic pneumonia SMQ (20000157): 
 ○ Angiolymphoid hyperplasia with eosinophilia (Narrow) 	
Listing: TEAE

Special Safety Topic	Definition / Derivation	Analysis / Summary / Listing
	
 ○ Eosinophilic bronchitis (Narrow) ○ Hypereosinophilic syndrome (Narrow) ○ Loeffler’s syndrome (Narrow) ○ Pulmonary eosinophilia (Narrow) ○ Pulmonary vasculitis (Narrow) 	
Inflammatory Bowel Disease (IBD)	
Inflammatory Bowel Disease (IBD) will be identified using the following subcategory and MedDRA PTs. The narrow terms are considered IBD. Medical reviews of patients identified with broad terms are needed for final determination of patients with IBD.
 
IBD (Narrow terms)
 
 1. Inflammatory Bowel Disease: Inflammatory bowel disease 2. Crohn’s Disease: Crohn’s disease 3. Ulcerative Colitis: Acute haemorrhagic ulcerative colitis; Colitis ulcerative; Proctitis ulcerative 
Non-Specific Terms: The PTs in this category are listed in Appendix 12 of the IXE PSAP V7
	
Listing: TEAE

Abbreviations: AE = adverse event; AESI = adverse events of special interest; ALP = alkaline phosphatase; CRF = case report form; eCRF = electronic case report form; FEAE = follow-up emergent adverse event; PT = preferred term; SAE = serious adverse event; TB = tuberculosis; TEAE = treatment emergent adverse event.

6.15.4. Clinical Laboratory Evaluation

Clinical laboratory assessments include hematology, serum chemistry, urinalysis, and safety related immune markers such as neutrophil counts. Continuous laboratory tests will be summarized as changes from baseline to last observation for patients who have both baseline and at least one post-baseline result for Period 2, Period 3, and Period 4, respectively:

- The scheduled visits/measurements will be included. The unscheduled visits and the repeated measurements taken at the same visit will be excluded.
- Both international system of unit (SI) and conventional unit will be summarized when different.
- For the safety population in the Blinded Treatment Period (Period 2), the comparisons between treatment groups will be conducted using an ANCOVA method with treatment group and baseline value in the model.
- Data will be analyzed based on original scale.

Laboratory test observed values at each visit (starting at baseline) and change from baseline to each scheduled visit, respectively, will be displayed in box plots for patients who have both a baseline and at least one post-baseline result. These box plots will be used to evaluate trends over time and to assess a potential impact of outliers on central tendency summaries.

The scheduled visits/measurements will be included. The unscheduled visits and the repeated measurements taken at the same visit will be excluded.

- The displays with both SI and conventional units will be provided when different.
- The following summary statistics will be included as a table below the box plot: number of patients with a baseline and at least one post-baseline result, mean, standard deviation, minimum, Q1, median, Q3, and maximum.
- Data will be summarized based on original scale.
- On the box plots of the laboratory test observed values, the lines of the reference ranges/limits (by using the large clinical trial population based reference limits, that is, Lilly reference ranges) will be added. In cases where limits vary across age and gender, the lowest of the high limits and the highest of the low limits will be used.
- The number and percentage of patients with a treatment-emergent or follow-up emergent abnormal, high, or low for laboratory tests will be summarized by treatment group for each study period. The comparisons between treatment groups will be conducted using Fisher's exact test for the safety population in the Blinded Treatment Period (Period 2). All scheduled, unscheduled and repeated measurements taken at the same visit will be included.
- In general, large clinical trial population based reference limits (that is, Lilly reference ranges) will be used to define the low and high limits since it is generally desirable for

limits used for analyses to have greater specificity (identify fewer false positive cases) than reference limits used for individual subject management. In the case when the reference limits based on the large clinical trial population is not available for a laboratory measure, performing lab reference ranges will be used. Alanine aminotransferase (ALT), aspartate aminotransferase (AST), total bilirubin, and alkaline phosphatase (ALP), neutrophils, leukocytes, platelets and lymphocytes, will not be included in the treatment-emergent abnormal, high, or low summary as a separate analysis addressing the risk of liver injury is described in Section 6.15.3.1 in which performing lab reference ranges are used.

- Note that the ranges are defined by a lower limit of normal (LLN) and an upper limit of normal (ULN). A result that is greater than or equal to the LLN and less than or equal to the ULN is considered to be within the normal ranges.
- For categorical laboratory tests:
 - Treatment-emergent abnormal value is defined as a change from normal at all baseline visits to abnormal at any time post-baseline during the Blinded Treatment Period.
 - Treatment-emergent abnormal value is defined as a change from normal at baseline to abnormal at any time post-baseline during the Open-label Treatment Period.
 - Follow-up emergent abnormal result is defined as a change from normal at baseline to abnormal at any time during the follow-up period.
- For continuous laboratory tests:
 - Treatment-emergent high value is defined as a change from a value less than or equal to the ULN at all baseline visits to a value greater than the ULN at any time post-baseline during the Blinded Treatment Period.
 - Treatment-emergent low value is defined as a change from a value greater than or equal to the LLN at all baseline visits to a value less than the LLN at any time post-baseline during the Blinded Treatment Period.
 - Treatment-emergent high value is defined as a change from a value less than or equal to the ULN at baseline to a value greater than the ULN at any time post-baseline during the Open-label Treatment Period.
 - Treatment-emergent low value is defined as a change from a value greater than or equal to the LLN at baseline to a value less than the LLN at any time post-baseline during the Open-label Treatment Period.
 - Follow-up emergent high value is defined as a change from a value less than or equal to the ULN at baseline to a value greater than the ULN at any time post-baseline during the follow-up period.

- Follow-up emergent low value is defined as a change from a value greater than or equal to the LLN at baseline to a value less than the LLN at any time post-baseline during the follow-up period.

A by-patient listing of laboratory test values will be provided. A listing of laboratory tests reference ranges (both large clinical trial population based reference limits and performing lab reference ranges) will be provided. By-patient listing of abnormal laboratory test results (criteria defined in the shift tables excluding the normal category) for parameters of special interest (hepatic, leukocytes and platelets) will be provided.

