9.6.2. Clinical Laboratory Tests

Laboratory assessments will be presented as mean changes from baseline and as incidence of treatment-emergent abnormal, high, or low laboratory values. Shift tables will be presented for selected parameters.

- For categorical lab tests:
 - Treatment-emergent abnormal value = a change from normal at all baseline visits to abnormal at any time postbaseline.
- For continuous lab tests:
 - Treatment-emergent high value = a change from a value less than or equal to the high limit at all baseline visits to a value greater than the high limit at any time postbaseline.

- Treatment-emergent low value = a change from a value greater than or equal to the low limit at all baseline visits to a value less than the low limit at any time postbaseline.

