6.15.4.1. Leukocytes (WBC) and Platelets

Further analyses will be conducted for total leukocytes, neutrophils, platelets, lymphocytes, monocytes, eosinophils, and basophils. Neutrophils will be defined as absolute neutrophils (derived by adding segmented neutrophils and band neutrophil). Shift table will be produced showing the number and percentage of patients shifting from baseline to a minimum post-baseline result in each relevant category by treatment group for Period 2, Period 3 and Period 4, respectively.

- Scheduled visits, unscheduled visits, and repeated measurements taken at the same visit will be included.
- Baseline is defined as the minimum result during the defined baseline period or baseline.
- Use the minimum non-missing post-baseline value within each study period.
- The parameters and categories are:
 - Leukocytes; $\geq 1 \times \text{LLN}$, $< 1 \times \text{LLN}$ to $\geq 3.0 \times 10^9/\text{L}$, $< 3.0 \times 10^9/\text{L}$ to $\geq 2.0 \times 10^9/\text{L}$, $< 2.0 \times 10^9/\text{L}$ to $\geq 1.0 \times 10^9/\text{L}$, and $< 1.0 \times 10^9/\text{L}$
 - Neutrophils (absolute neutrophils); $\geq 1 \times \text{LLN}$, $< 1 \times \text{LLN}$ to $\geq 1.5 \times 10^9/\text{L}$, $< 1.5 \times 10^9/\text{L}$ to $\geq 1.0 \times 10^9/\text{L}$, $< 1.0 \times 10^9/\text{L}$ to $\geq 0.5 \times 10^9/\text{L}$, and $< 0.5 \times 10^9/\text{L}$
 - Platelets; $\geq 1 \times \text{LLN}$, $< 1 \times \text{LLN}$ to $\geq 75.0 \times 10^9/\text{L}$, $< 75.0 \times 10^9/\text{L}$ to $\geq 50.0 \times 10^9/\text{L}$, $< 50.0 \times 10^9/\text{L}$ to $\geq 25.0 \times 10^9/\text{L}$, and $< 25.0 \times 10^9/\text{L}$
 - Lymphocytes; $\geq 1 \times \text{LLN}$, $< 1 \times \text{LLN}$ to $\geq 0.8 \times 10^9/\text{L}$, $< 0.8 \times 10^9/\text{L}$ to $\geq 0.5 \times 10^9/\text{L}$, $< 0.5 \times 10^9/\text{L}$ to $\geq 0.2 \times 10^9/\text{L}$, and $< 0.2 \times 10^9/\text{L}$
- The above LLNs are defined as:
 - Leukocytes: $\text{LLN} = 4.0 \times 10^9/\text{L}$
 - Neutrophils: $\text{LLN} = 2.0 \times 10^9/\text{L}$
 - Lymphocytes: $\text{LLN} = 1.1 \times 10^9/\text{L}$
 - Platelets: $\text{LLN} = 150 \times 10^9/\text{L}$
- With additional categories:

- Decreased; post-baseline category < baseline category
- Increased; post-baseline category > baseline category
- Same; post-baseline category = baseline category.

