The change from minimum baseline to minimum post-baseline result for each of these leukocytes and platelets will be summarized graphically using a box plot for Period 2, Period 3, and Period 4, respectively.

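### SAP 6.15.4 drops leukocytes, neutrophils, platelets and lymphocytes from the treatment-emergent high/low summary for a liver-injury reason that does not fit them, so the incidence of high values planned in protocol 9.6.2 is not produced

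*SAP*

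**What the plan says.** Protocol 9.6.2 states: "Laboratory assessments will be presented as mean changes from baseline and as incidence of treatment-emergent abnormal, high, or low laboratory values". It defines treatment-emergent high and low for continuous tests and exempts no analyte. It adds shift tables for selected parameters.

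SAP 6.15.4 turns this into the number and percentage of patients with treatment-emergent or follow-up-emergent abnormal, high or low results. The summary is by treatment group and study period, uses scheduled, unscheduled and repeat measurements, and has Fisher's exact test in Period 2. The same section then says that ALT, AST, total bilirubin and ALP, together with "neutrophils, leukocytes, platelets and lymphocytes, will not be included in the treatment-emergent abnormal, high, or low summary as a separate analysis addressing the risk". It completes the reason by saying that an analysis "of liver injury is described in Section 6.15.3.1 in which performing lab reference ranges are used".

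SAP 6.15.4.1 gives the blood counts their own analysis: "Shift table will be produced showing the number and percentage of patients shifting from baseline to a minimum post-baseline result", for Periods 2, 3 and 4, with the rule "Use the minimum non-missing post-baseline value within each study period". For all four counts the categories start at or above LLN and go down. Period-specific box plots follow: "The change from minimum baseline to minimum post-baseline result for each of these leukocytes and platelets will be summarized graphically using a box plot".

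SAP 6.15.4 also plans a listing of abnormal results for hepatic, leukocyte and platelet parameters, with "criteria defined in the shift tables excluding the normal category".

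**The concern.** The exclusion sentence covers two groups of tests but gives a reason for only one. The liver tests lose their place in the high/low summary because SAP 6.15.3.1 analyses their elevations separately. The four counts lose theirs with no reason that applies to them, and what they receive instead looks in one direction only. The protocol's planned incidence of high values is therefore dropped for leukocytes, neutrophils, platelets and lymphocytes without being acknowledged.

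At stake is completeness of safety reporting. Infections are an adverse event of special interest (protocol 8.2.2), so a reader of the report could reasonably ask how many patients per arm developed a high leukocyte or neutrophil count. No planned table answers that.

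**Working it through.** The documents give no figure to reproduce, so the check sets the planned outputs side by side.

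**Does the stated reason fit?** SAP 6.15.3.1 (Table RHBQ.6.6) tabulates elevations of ALT, AST, bilirubin and ALP. For blood counts it has cytopenia adverse events, which are low-side, and an infection listing that carries the minimum Period 2 value of these four counts. Neither covers high values. The remark about performing-laboratory ranges does not fit either, because 6.15.4.1 uses fixed LLNs (leukocytes 4.0, neutrophils 2.0, lymphocytes 1.1, platelets 150, all ×10⁹/L).

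**What do the planned outputs show for the four counts?**

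| SAP output | Shows upward values | Unscheduled and repeat values | Counts patients above ULN | Compares arms in Period 2 |
|---|---|---|---|---|
| High/low summary (6.15.4) | four counts excluded | – | – | – |
| Shift table (6.15.4.1) | no: minimum value, top category at or above LLN | included | no | no test named |
| Minimum-to-minimum box plot (6.15.4.1) | only if the minimum rises | not stated | no | no |
| Abnormal-result listing (6.15.4) | no: same categories | not stated | no | no |
| Change to last observation (6.15.4) | on average | excluded | no | ANCOVA |
| By-visit box plots and table (6.15.4) | yes: Q3, maximum; reference limits on observed-value plots | excluded | no | no |
| Listing of all laboratory values (6.15.4) | yes | no restriction stated | no | no |

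The Increased label in the shift table means movement among the low-side categories, so it does not identify a value above ULN.

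**Illustration.** Take neutrophils of 4 at baseline, 25 at Week 4 and 4 at Week 12 (×10⁹/L). Assume ULN lies between 4 and 25; the SAP does not print it.

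- Shift table: baseline 4 is above 2.0, so top category. Post-baseline minimum = min(25, 4) = 4, again top category. Label: Same.
- Abnormal-result listing: not flagged.
- Change to last observation: 4 − 4 = 0.
- By-visit table: the Week 4 maximum is at least 25, so the value is visible.
- If the 25 came from an unscheduled panel, which protocol Appendix 3 allows, the by-visit table omits it and only the full listing shows it.

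**Extent.** 4 analytes × 3 periods (2, 3 and 4) = 12 high-value incidence summaries not produced, and 4 Fisher comparisons of high values in Period 2 not made.

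**The case against.** The case for leaving the SAP alone has several parts.

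- The declared risk for these counts is low. Cytopenias are the adverse event of special interest, and the protocol's monitoring and discontinuation rules for these counts are low-side. A shift to the minimum matches that. This stands, and it is why the shift tables should be kept and why the point is minor.
- Infections are analysed directly, with Fisher's exact test in Period 2, and clinically significant laboratory findings that result in a diagnosis are reported as adverse events. This also stands. The documents name no safety concern about high values of these counts.
- Protocol 9.2 leaves full detail to the SAP, and lets changes that do not alter a principal feature be described and justified in the CSR. So a departure from 9.6.2 is permissible. However, the SAP states no departure and gives no reason that applies. The shift tables in 9.6.2 are planned as well as the incidence summary and do not replace it.
- The reason may be a drafting slip, with the counts added to a sentence about liver tests. That is plausible, but correcting the cross-reference alone would still leave high values uncounted.

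A reader might also infer that high blood counts are never tabulated or compared, or appear only in box plots. The documents do not support that. SAP 6.15.4 keeps hematology in the change-to-last-observation summary with ANCOVA in Period 2, tabulates Q3 and the maximum by visit, draws reference limits on the observed-value plots, and lists every patient's values. Nor is all hematology affected: monocytes, eosinophils, basophils, hemoglobin and the remaining tests are not in the exclusion.

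**Conclusion.** The point holds in a narrow form. For four analytes, the SAP omits the incidence of treatment-emergent and follow-up-emergent high values that it otherwise provides, and the only reason it gives does not apply to them. The outputs that remain do not fill the gap: none counts patients above ULN, and the ANCOVA and by-visit outputs leave out unscheduled and repeat measurements.

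This rests on the SAP text alone. No expected frequency of high counts can be derived from the documents, so nothing can be said about how many patients would be affected. Severity is minor: it is a gap in safety reporting and an unexplained difference from protocol 9.6.2, with no bearing on the primary or secondary efficacy conclusions.

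**What to change.** In SAP 6.15.4:

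1. Limit the exclusion, and its liver-injury rationale, to ALT, AST, total bilirubin and ALP.
2. Restore leukocytes, neutrophils, platelets and lymphocytes to the treatment-emergent and follow-up-emergent high summary, with Fisher's exact test in Period 2, using the definitions already in that section.
3. Add high values of these counts to the abnormal-result listing.
4. Keep the low-value shift tables as they are, and refer to 6.15.4.1 for them.

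The cost is revised wording and a few rows in an existing table and listing; no new data are needed. If the sponsor prefers to keep the exclusion, the SAP should say so as a departure from protocol 9.6.2, give a reason that applies to blood counts, and carry that reason into the CSR.
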